7.5 Covariates

Not applicable. All data will be summarized by means of descriptive statistics.

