9.1 Primary Efficacy Variable

The primary efficacy variable is the number of days alive and ventilator-free days, defined as the number of days the subject is not receiving mechanical ventilation over the 21 days following randomization. Mechanical ventilation is defined as invasive and non-invasive. Subject is defined free of mechanical ventilation after 12 hours from the suspension of either invasive or non-invasive ventilation.

Subjects who die or are mechanically ventilated longer than this period are assessed as zero ventilator-free days.

Notes:

Subjects with at least 12 hours of suspension of ventilation either invasive or non-invasive ventilation will be flagged. Then duration will be calculated within the flagged subject's subset, as below:

- Ventilator-free days = 21-[MAX (End date of invasive ventilation; End date of non-invasive ventilation)] – Date of randomisation + 1.

Descriptive summaries of the number of ventilator-free days will be presented by treatment group.

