9.2 Key Secondary Efficacy Variable

The key secondary efficacy variable is the percentage of subjects alive and free of respiratory failure (i.e., need for mechanical ventilation, ECMO, non-invasive ventilation, or high-flow nasal cannula oxygen delivery) at **Day 28**.

Notes:

The subject will be defined alive and free of respiratory failure if:

- On Patient Status form at “D28-FU” visit, the subject is still alive

AND

- On Ventilatory Support form, if start date is not missing, max (end date) for any ventilator type > date of “D28 – FU” visit

The percentage will be summarized.

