9.3 Others Secondary Efficacy Variables

9.3.1 Number of Days Alive and Ventilator-free at Day 28

First, within subject with a start date filled in the ventilator support form, subjects with at least 12 hours of suspension of ventilation either invasive or non-invasive ventilation will be flagged. Then duration will be calculated within the flagged subject's subset, as below:

- Ventilator-free days = 28-[MAX (End date of invasive ventilation; End date of non-invasive ventilation)] – Date of randomisation + 1].

Subjects who die or are mechanically ventilated longer than this period are assessed as zero ventilator-free days.

Number of ventilator-free days will be described at Day 28.

9.3.2 Mortality at Day 21 and Day 28

The number and proportion of deaths at Day 21 and Day 28 will be presented for both groups.

9.3.3 Number of Days Alive and Free from invasive and Non-Invasive ventilation at Day 21 and Day 28

For Day 21:

First, subjects with at least 12 hours of suspension of ventilation will be flagged by type (i.e. one flag for Non-Invasive, and one for Invasive). Then duration will be calculated within the flagged subject's subsets, as below:

- Invasive ventilation-free days = 21-(End date of invasive ventilation) – Date of randomisation + 1].
- Non-invasive ventilation-free days = 21-(End date of non-invasive ventilation) – Date of randomisation + 1].

If subject never started a non-invasive ventilation then the value will be set to 21 days.

For Day 28:

First, subjects with at least 12 hours of suspension of ventilation will be flagged by type (i.e. one flag for Non-Invasive, and one for Invasive). Then duration will be calculated within the flagged subject's subsets, as below:

- Invasive ventilation-free days = 28-(End date of invasive ventilation) – Date of randomisation + 1].

- Non-invasive ventilation-free days = 28-(End date of non-invasive ventilation) – Date of randomisation + 1].

If subject never started a non-invasive then the value will be set to 28 days.

Subjects who die or are mechanically ventilated longer than this period are assessed as zero ventilator-free days.

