10.4 Laboratory Parameters

Laboratory parameters actual values and change from baseline will be presented using descriptive statistics by timepoint for each treatment group.

An individual subject listing will also be provided for laboratory data.

11 Other Analyses

No other analyses planned. All other data collected in the eCRF will be listed.

12 Changes in the Planned Analyses from Study Protocol

As this study is specifically linked to the COVID-19 pandemic situation, as there was a global improvement in the countries (US, UK, Italy) where the study was done during 2021 (vaccines against COVID-19, better treatment, variant less contagious...), the recruitment was lower than expected and the study was closed before reaching the target sample size of 70 subjects.

As a consequence all statistical analysis planned in the protocol were not done considering the low sample size:

- Statistical Analysis of Days Alive and Free from Ventilation at Day 21
- Subjects alive and free of respiratory failure at Day 28.
- Statistical Analysis of Days Alive and Free from Invasive Ventilation Day 28
- Statistical Analysis of Days Alive and Free from Invasive Ventilation at Day 21 and Day 28
- Statistical Analysis of Days Alive and Free from Non-Invasive Ventilation at Day 21 and Day 28
- Statistical Analysis of Mortality at Day 21 and Day 28
- Statistical Analysis of Proportion of Subjects with Improvement in Severity Status at Day 28/Discharge
- Statistical Analysis of Change from Baseline in pao₂/fio₂ Ratio at Each Timepoint
- Statistical Analysis of Proportion of Subjects with pao₂/fio₂ Ratio Improvement >20% Compared to Baseline at Each Timepoint
- Statistical Analysis of Change from Baseline in fio₂ at Each Timepoint
- Statistical Analysis of Length of ICU Stay (Days) at Day 28
- Statistical Analysis of Proportion of Subjects Alive and Out of ICU at Day 28
- Statistical Analysis of Delta SOFA Score at Day 3 and Day 28/ Discharge
- Statistical Analysis of Delta SOFA Sub Score at Day 3 and Day 28/Discharge
- Statistical Analysis of Proportion of Subjects Alive and Organ Failure Free at Day 28/Discharge

ITT definition was changed from “all randomised patients (analysed as randomised)” to “all randomised subjects who have at least one post baseline efficacy data analysed as randomised”.

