Table 14.1.5.1	Medical and Surgical History (Safety Set)	MHT001	- Overall column should be displayed. - Replace <Condition/Procedure> by 'Medical History'.	Add the footnote: [1] System Organ Class and Preferred Term are coded using MedDRA Version 23.0. Source: Listing 16.2.4.4
Table 14.1.5.2	Concomitant Diseases (Safety Set)	MHT001	- Overall column should be displayed. - Replace <Condition/Procedure> by 'Concomitant Disease'	Add the footnote: [1] System Organ Class and Preferred Term are coded using MedDRA Version 23.0. Source: Listing 16.2.4.5
Table 14.1.5.3	Prior Procedures (Safety Set)	MHT001	- Overall column should be displayed. - Replace <Condition/Procedure> by 'Prior Procedure'	Add the footnote: [1] System Organ Class and Preferred Term are coded using MedDRA Version 23.0. Source: Listing 16.2.4.6
Table 14.1.5.4	Maintained Procedures (Safety Set)	MHT002		Same as Table 14.1.5.3
Table 14.1.5.5	Concomitant Procedures (Safety Set)	MHT002		Same as Table 14.1.5.3
Table 14.1.6.1	Prior Medications (Safety Set)	CMT001	Overall column should be displayed.	Add the footnote: [1] ATCs and Preferred Name are coded using WHO-DD March 2020. Source: Listing 16.2.4.7
Table 14.1.6.2	Maintained Medications (Safety Set)	CMT002	Overall column should be displayed	Same as Table 14.1.6.1
Table 14.1.6.3	Concomitant Medications (Safety Set)	CMT002	Overall column should be displayed	Same as Table 14.1.6.1

Table Number	Table Title	Template Code	Notes	Footnotes/Source Listing Number
Table 14.2.1	Summary of Number of Days Alive and Ventilator-free at Day 21 (Intention-To-Treat)	TPT002	
 - Display the number of days alive and Ventilator-free at Day 21 - Remove '95% CI for Mean', 'n geometric', 'Geometric mean' categories. 	Add the footnote: [1] Subjects who die or are mechanically ventilated longer than this period are assessed as zero ventilator-free days. Source: Listing 16.2.6.2-b
Table 14.2.2	Summary of Proportion of Subjects Alive and Free of Respiratory Failure at Day 28 (Intention-To-Treat)	TPT006	
 - There is only one timepoint to display: Day28. - Do not present 'At Any timepoint' line. - Do not display 'Visit' on the title line. 	Source: Listing 16.2.6.2-b

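### After early closure the SAP gives only by-arm summaries for ventilator-free days, the key secondary endpoint and mortality; low N does not justify dropping an unadjusted between-arm difference with its interval

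*SAP*

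**What the plan says.** **Protocol.** Section 12.3.4 compares ventilator-free days over 21 days between groups with an ANOVA on treatment, age and country; it names no interval. Section 12.3.4.1 (key secondary) and section 12.3.5 (mortality) use logistic regression and promise a difference in proportions with a 95% interval.

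**SAP.** Section 12 reports that the study stopped short of 70 subjects: "As a consequence all statistical analysis planned in the protocol were not done considering the low sample size". Its list includes all the endpoints above. Section 7.5 reads: "Not applicable. All data will be summarized by means of descriptive statistics". What is left is:

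- 9.1, primary: "Descriptive summaries of the number of ventilator-free days will be presented by treatment group".
- 9.2, key secondary: "The percentage will be summarized".
- 9.3.2, mortality: "The number and proportion of deaths at Day 21 and Day 28 will be presented for both groups".

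In section 16.1 the notes for Table 14.2.1 say: "Remove '95% CI for Mean', 'n geometric', 'Geometric mean' categories". The notes for Tables 14.2.2 and 14.2.4 ask for no between-arm difference.

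Some wording from a comparative plan survives. Section 7.1 keeps a rule for tests and 95% intervals where applicable, section 9 still refers to efficacy comparisons between groups, and section 13.2.2 keeps formats for differences, intervals and p-values. None of it specifies an estimate for these endpoints.

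**The concern.** The reason given is low sample size. That supports removing hypothesis tests, which would have little power, and models with age and country terms, which may fit poorly with few patients. It does not support removing the crude difference and its interval, because the interval is what shows a reader how little a small trial can exclude. Two means or two percentages side by side invite the reader either to over-read the gap or to dismiss it. The report of a randomised proof-of-concept trial would then state no treatment effect, with its precision, on its primary endpoint, its key secondary endpoint or mortality.

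**Working it through.** **1. The plan's own figure.** Inputs from SAP section 5: 42 and 28 patients, difference 4 days (11 against 7), SD 5.5, two-sided alpha 0.05, t-test. Noncentrality = 4 / (5.5 × √(1/42 + 1/28)) = 4 / (5.5 × 0.2440) = 2.98 on 68 df. Power is 83.6% by the noncentral t and 84.6% by the normal approximation. The stated 84% reproduces.

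**2. Precision of the missing estimates.** The documents do not give the achieved N, so every arm size below is an assumption at the 3:2 ratio. SD 5.5 is the planning value; SD 8 is an added assumption, because many zeros may widen the spread.

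Welch half-width = t(0.975, df) × SD × √(1/n1 + 1/n2), equal SDs. For 12/8: df 15.2, t = 2.130, and 2.130 × 5.5 × 0.4564 = 5.35 days. The Newcombe half-widths cover all counts with both observed proportions between 25% and 60% (assumed).

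| Arms (assumed) | Welch, SD 5.5 (days) | Welch, SD 8 (days) | Interval if 4 days is observed (SD 5.5) | Newcombe (points) |
|---|---|---|---|---|
| 36/24 | 2.9 | 4.2 | 1.1 to 6.9 | 22–24 |
| 21/14 | 3.9 | 5.7 | 0.1 to 7.9 | 29–30 |
| 12/8 | 5.3 | 7.8 | −1.3 to 9.3 | 36–38 |
| 6/4 | 8.5 | 12.4 | −4.5 to 12.5 | 46–47 |

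**3. Do the methods hold at these sizes?** Exact Newcombe coverage, with true proportions from 0.30 to 0.60 in steps of 0.05, is 94.4–95.6% at 21/14, 93.7–96.0% at 12/8 and 90.7–96.8% at 6/4. Welch coverage was simulated on 0–21-day data with assumed means of 7 and 11 days, 30–50% zeros in control and 10–40% in the treated arm. It was 94.8–95.1%, 94.7–95.1% and 94.1–96.0% at the same sizes.

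**4. The derivations that feed any estimate.**

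- *Section 9.1.* The formula begins "Ventilator-free days = 21-[MAX (End date of invasive ventilation; End date of non-invasive ventilation", closes its bracket there, and then subtracts the randomisation date as well. Taking both dates from 21 is not a day count. If ventilation ends on Study Day 10 (end minus randomisation = 9), one repair gives 21 − (9 + 1) = 11 days and the other gives 21 − 9 + 1 = 13. The closing bracket in section 9.3.1 falls after the + 1, which supports 11.
- *Section 9.2.* A subject counts as free of respiratory failure if alive and "max (end date) for any ventilator type > date of" the Day 28 visit. That selects support ending after the visit, the reverse of the endpoint. Assumed example at 12/8: 3/3 deaths, 3/2 still supported, 6/3 free. As defined, the result is 6/12 against 3/8 = +12.5 points (Newcombe −27.8 to +46.8). As written, it is 3/12 against 2/8 = 0.0 (−37.7 to +33.4), but only if the supported patients have end dates after the visit. If they are recorded as ongoing with no end date, the written rule gives 0/12 against 0/8.

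**The case against.** The best defence is that this is a disclosed and conventional choice. Section 12 announces the closure and lists what was withdrawn, and descriptive reporting of a phase II trial that closed early is defensible. Section 7.8 gives n, mean, SD, median and range by arm, and counts are reported, so a reader can rebuild a crude interval. The protocol named no interval for the primary endpoint. At 6/4 an interval is close to uninformative. All of this stands and limits the weight of the point. It also shows that the estimates need no new data, and it does not explain why the sponsor's own report should omit them.

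A reader might infer more than the documents support:

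- *Concealment.* The change is set out in section 12.
- *No information on uncertainty.* By-arm n and SD are given; the difference and its interval are what is missing.
- *No between-group description of any endpoint.* Section 9.3.10 describes the between-group difference in SOFA change, though without an interval.
- *Templates that certainly hold no interval.* TPT002 and TPT006 belong to a sponsor library that was not supplied. The SAP text and visible table notes request no between-arm difference, and the descriptive-only statements agree with that.

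Newcombe is not the only acceptable method, and a bootstrap or rank-based interval is arguable for ventilator-free days. What matters is naming one method per endpoint type before computing.

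**Conclusion.** The point holds as a reporting gap that should be closed. For ventilator-free days at Day 21, the key secondary endpoint and Day 21 and Day 28 mortality, the SAP replaces the planned between-group analyses with by-arm summaries and plans no difference or interval. This rests on the text and does not depend on the achieved N.

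How informative the intervals would be does depend on N. At SD 5.5 the half-width is below the 4-day design difference at 36/24 (2.9) and just below it at 21/14 (3.9), and above it at 12/8 (5.3) and 6/4 (8.5). At SD 8 it exceeds 4 days at all four sizes. The errors in 9.1 and 9.2 are separate defects that also distort the by-arm summaries, so they must be corrected before any difference is computed.

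**What to change.** 1. **Derivations first.** In 9.1 use 21 − (last end date − randomisation date + 1). In 9.2 count a subject as free only if alive, with the last end date before the Day 28 visit and no support ongoing.
2. **Estimates.** In 9.1, 9.2, 9.3.2 and Tables 14.2.1, 14.2.2 and 14.2.4 add the unadjusted difference, poractant alfa minus control, with a two-sided 95% interval and no p-value, labelled as estimation. State one method per endpoint type in advance, for example Welch for days and Newcombe for proportions, and note that Newcombe coverage can fall to about 91% at 6/4.
3. **Population.** Use all randomised patients with known status, as in the protocol's ITT. SAP 6.2 narrows ITT to subjects with post-baseline efficacy data, although SAP 7.13 equates it with the randomised set. Score deaths as already stated, and report the number missing by arm.
4. **Record.** Enter the change in SAP 12 and align the leftover wording in 7.1, 9 and 13.2.2. If the database is locked, report the same estimates in the clinical study report as post hoc; SAP section 1 already sends deviations there.

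**Cost.** Four estimates, three table shells, two corrected derivations and short text edits; no new data. The intervals will be wide and could be over-read as tests, which is why the estimation label matters.

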9.2 Key Secondary Efficacy Variable

The key secondary efficacy variable is the percentage of subjects alive and free of respiratory failure (i.e., need for mechanical ventilation, ECMO, non-invasive ventilation, or high-flow nasal cannula oxygen delivery) at **Day 28**.

Notes:

The subject will be defined alive and free of respiratory failure if:

- On Patient Status form at “D28-FU” visit, the subject is still alive

AND

- On Ventilatory Support form, if start date is not missing, max (end date) for any ventilator type > date of “D28 – FU” visit

The percentage will be summarized.

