8. EFFICACY ASSESSMENTS

Primary Endpoint

The primary outcome variable will be the number of days alive and ventilator-free defined as the number of days the patient is alive and not receiving mechanical ventilation over the **21 days** following randomisation.

Mechanical ventilation will be defined as invasive and non-invasive. Patient will be defined free of mechanical ventilation after 12 hours from the suspension of either invasive and non-invasive ventilation. Patients who die or are mechanically ventilated longer than this period are assessed as zero ventilator-free days.

Key secondary endpoint

- Percentage of patients alive and free of respiratory failure (i.e., need for mechanical ventilation, ECMO, non-invasive ventilation, or high-flow nasal cannula oxygen delivery) at **Day 28**

Secondary endpoints

- Number of days alive and ventilator-free at **Day 28**
- Mortality at **Day 21** and **Day 28**
- Number of days alive and free from invasive ventilation at **Day 21** and **Day 28**
- Number of days alive and free from non-invasive ventilation (NIV) at **Day 21** and **Day 28**
- Percentage of patients with improvement in severity status defined as a decrease in the severity score at **Day 28 or Discharge**, whichever comes first. Severity score will be defined as Mild, Moderate, Severe or Death based on PaO₂/FiO₂ ratio and patient status at Day 28 and numerically rated from 1-4 respectively:

Severity	Variable	Criteria
Mild - 1	PaO ₂ /FiO ₂ Ratio	200 mmHg < PaO ₂ /FIO ₂ ≤ 300 mmHg
Moderate - 2	PaO ₂ /FiO ₂ Ratio	100 mmHg < PaO ₂ /FIO ₂ ≤ 200 mmHg
Severe - 3	PaO ₂ /FiO ₂	Ratio PaO ₂ /FIO ₂ ≤ 100 mmHg
Death - 4	Patient Status	Yes/No

- Change from baseline in PaO₂/FiO₂ ratio at **6 and 12 hours following administration of each dose** in the treated group and at the similar timepoints in the control group (6, 12, 30, 36, 54 and 60 hours after randomisation)

Clinical Study Code No.: CLI-050000-04	Version No.: 4.0
EUDRACT No.: 2020-002632-75 – IND No: 153286	Date: 02 MAR 2021

- Change from baseline in PaO₂/FiO₂ ratio at additional timepoints (i.e. every 24 hours after treatment/randomisation until the patient is discharged from the ICU)
- Percentage of patients alive and with PaO₂/FiO₂ improvement of >20% at **6 and 12 hours following administration of each dose** in the treated group and at similar timepoints in the control group (6, 12, 30, 36, 54 and 60 hours after randomisation)

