4.1.2 Secondary Efficacy Variables

4.1.2.1 Key Secondary Efficacy Variable

- Percentage of subjects alive and free of respiratory failure (i.e., need for mechanical ventilation, ECMO, non-invasive ventilation, or high-flow nasal cannula oxygen delivery) **at Day 28**.

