7.4 Handling of Missing Data

In general, except as described below, missing data will not be imputed.

The number of subjects with missing data will be presented under a “Missing” category. Unless otherwise stated, missing values will not be included in the denominator count when calculating percentages.

When quantitative variables are being summarized, only the non-missing values will be evaluated for calculating summary statistics.

Other critical missing data, if any, will be discussed during the review of the data before database lock. Decisions will be fully documented in the Data Review Report.

Medications: Missing/Incomplete Date

In case of missing or incomplete dates not directly allowing allocation to any category of medications, a worst-case allocation will be done according to the available parts of the start and the stop dates. The medications will be allocated to the first category allowed by the available data, according to the following order:

1. Concomitant medication;
2. Maintained medication;
3. Prior medication.

Procedures: Missing/Incomplete Date

In case of missing or incomplete dates not directly allowing allocation to any category of procedure, a worst-case allocation will be done according to the available parts of the start and the stop dates. The procedure will be allocated to the first category allowed by the available data, according to the following order:

1. Concomitant procedure;
2. Maintained procedure;
3. Prior procedure.

Adverse Events (AEs): Missing/Incomplete Date

In case of missing or incomplete date/time not directly allowing allocation to any of the category of AEs, a worst-case allocation will be done according to the available parts of the start and the stop dates/times. The AE will be allocated to the first category allowed by the available data, according to the following order:

1. Treatment emergent;
2. Pre-treatment.

Adverse Events (AEs): Missing Severity

In case of missing severity, the severity will not be imputed and will be reported as “Missing”. For the table of TEAEs by maximum severity, the maximum severity will be considered as the maximum of the non-missing severities for the relevant subject and preferred term.

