9.3.7 Change from Baseline in FiO_2 at each Timepoint After Treatment

Actual values and change from baseline in FiO_2 at 6 and 12 hours following each treatment medication administration in the poractant alfa group and then each 24 hours till the subject is discharged from the ICU and similar timepoints in the control group (defined as 6 and 12 hours after randomization for Day 1, 30 and 36 hours after randomization for Day 2 and 54 and 60 hours post randomization for Day 3 and then each 24 hours till the subject is discharged from the ICU) will be described.

9.3.8 Length of ICU Stay at Day 28

The length of ICU stay (in days) will be calculated as: MIN (date of ICU discharge, date of Day 28) – date of ICU entrance + 1.

In case of readmission in ICU, the duration of the primary one and the readmission will be added. Lengths of ICU stay will be presented in total.

Subjects who die or are mechanically ventilated longer than this period will be assigned with a 28 days length value.

Those subjects will be identified using:

- On Study Completion form, death date is filled and $< \text{MIN} (\text{date of ICU discharge, date of Day 28})$
- On Ventilatory Support form the subtype Invasive- Mechanical ventilation is ticked and $(\text{End Date} - \text{Start Date}) + 1 > 28 \text{ Days}$ or if Ongoing is ticked (i.e. subject still under mechanical ventilation at the end of the Study).

In case of multiple sessions of Invasive- Mechanical ventilator support without any discharge in between the MIN start date and the MAX end date will be taken into account.

It will be presented using descriptive statistics by treatment group.

A graph displaying the mean and SD for each timepoint (until the subject is discharged from ICU) will be also provided for each treatment group.

9.3.9 Percentage of Subjects Alive and Out of ICU at Day 28

The subject will be defined alive and out of ICU at Day 28 if:

- On Patient Status form at "D28 – FU" visit, the subject is still alive

AND

- Date of ICU discharge Visit < Date of “Day 28 – FU” visit

The percentage will be summarized.

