13.1 Software

SAS version 9.4 will be used to perform all the statistical analyses.

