Listing 16.2.6.1	Ventilatory Support (Intention-To-Treat Set)		
The following columns will be presented:
 
 - Subject ID - Randomized Treatment - Actual Treatment - Ventilator Type - Start Date/Time [Day] - Stop Date/Time [Day] or Ongoing - Duration of Ventilatory Support (Days) – displayed by Type of Support (Invasive or Not Invasive) - Overall Duration of Ventilator Support 	Add the footnotes: [1]: Duration of ventilatory support have been calculated as the difference between end date and start date +1. [2]: Overall duration of ventilatory support has been calculated as the difference between the maximum end date (between invasive and non-invasive ventilation) and start date +1.

Listing Number	Listing Title	Template Code	Notes	Footnotes
Listing 16.2.6.2-a	Ventilatory Parameters by Timepoint (Intention-To-Treat Set)	VSL002	
 - Remove 'Analysis Period' - Display 'Assessment date/Time [Study Day]' instead of 'Assessment date/time [study day / study day in period]' - Do not display [H] flag in Change from baseline column - Skip the last column (Change from pre-dose) - In Test <Unit> column, display: 
 - FiO2 (%) - Mean Arterial Pressure (mmHg) - Dynamic Compliance (ml/cmH₂O) - Static Compliance (ml/cmH₂O) - PaO₂/FiO₂ Ratio - Tidal Volume (ml/kg BW) - Respiratory Rate (/min) - Peak Inspiratory Pressure - PIP (cmH₂O) - Plateau Pressure (cmH₂O) - Positive End-Expiratory Pressure - PEEP (cmH₂O) - Blood Flows (L/min) - Sweep Gas Flows (L/min) - Add a last column displaying PaO₂/FiO₂ Ratio Improvement (<20%, >=20% or death) 	Add the footnotes: [1]: Baseline=Y flags baseline value [2]: Use=Y: included in the analysis [3] Duplicated data reported twice at 2 different timepoints are reported at the first occurrence for post dose/post randomisation and at the last occurrence for pre dose/pre randomisation.

Listing Number	Listing Title	Template Code	Notes	Footnotes

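### SAP 9.2 reverses the inequality in the key secondary endpoint: survivors weaned before the Day 28 visit would be counted as not free of respiratory failure

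*SAP*

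**What the plan says.** Protocol section 8 defines the key secondary endpoint, assessed at Day 28, as "Percentage of patients alive and free of respiratory failure (i.e., need for mechanical ventilation, ECMO, non-invasive ventilation, or high-flow nasal cannula oxygen delivery"). SAP 4.1.2.1 repeats it ("Percentage of subjects alive and free of respiratory failure"), and so does the opening sentence of SAP 9.2.

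The notes in SAP 9.2 then give the derivation. A subject is a success if two conditions both hold: the Patient Status form shows the subject alive at the D28-FU visit, and on the Ventilatory Support form, "if start date is not missing, max (end date) for any ventilator type > date of" that visit.

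Three other places bear on the rule:

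- SAP 9.3.9 derives the parallel endpoint, alive and out of ICU at Day 28, with the opposite sign: "Date of ICU discharge Visit < Date of" the Day 28 visit.
- SAP 9.3.8 shows that the Ventilatory Support form has an ongoing option: "if Ongoing is ticked (i.e. subject still under mechanical ventilation at the end of the Study"). Listing 16.2.6.1 likewise shows "Stop Date/Time [Day] or Ongoing".
- SAP 12 drops the planned statistical analysis of this endpoint. Section 9.2, Table 14.2.2 and Listing 16.2.6.2-b keep the derivation and the percentages.

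**The concern.** The direction of the comparison is the opposite of what the endpoint means. A patient who came off all support on Day 10 and is alive at Day 28 is the success the endpoint is meant to count, yet this patient fails the second condition. A patient whose support ended after the visit, and who was therefore on support at the visit, meets it.

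Table 14.2.2 reports the trial's only key secondary endpoint. With formal testing removed (SAP 7.5 and 12), the percentage in each arm is all that will be reported for it. A programmer who follows the final SAP produces a wrong table. One who quietly corrects the sign departs from the SAP, and SAP section 1 says that such departures are to be explained in the study report.

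**Working it through.** The plan gives no figure for this endpoint, so there is none to reproduce. The check is a reading of the rule, a truth table, and an illustration of size.

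**Can the clause be read another way?**

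- It cannot be a definition of failure. Its lead-in defines success, and it is joined by AND to being alive.
- The qualifier about a non-missing start date exempts only patients with no recorded support. Protocol 4.2 requires every patient to be intubated and ventilated, and protocol 7.1.1 has the ventilation start time recorded in both groups, so the exemption should be empty.
- A text-extraction error is unlikely, since the signs in 9.3.8 and 9.3.9 read sensibly.
- No other section corrects the rule. SAP 12 lists only a dropped analysis, not a changed definition.

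**Truth table for a survivor, D28-FU visit on Day 28.** SAP 13.1 states that "SAS version 9.4 will be used to perform all the statistical analyses". In SAS a missing date compares as lower than any date, and MAX ignores missing values; this is general software behaviour and is not stated in the SAP.

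| Survivor | Endpoint meaning | 9.2 as written (>) | Sign reversed only (<) | Proposed rule |
|---|---|---|---|---|
| A. Invasive ends D10 | free | **not free** | free | free |
| B. Invasive ends D10, NIV ends D20 | free | **not free** | free | free |
| C. Invasive ongoing, end date blank | not free | not free | **free** | not free |
| D. Invasive ends D10, second record ongoing and blank | not free | not free | **free** | not free |
| E. On support, end date D35 entered | not free | **free** | not free | not free |

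The written rule is wrong in A, B and E. Reversing the sign alone is wrong in C and D. Deaths are coded correctly throughout, by the first condition. A last end date on Day 28 itself is not free under a strict < and free under ≤, so the tie has to be settled in words.

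**Conflict with SAP 9.3.1.** Take survivor A and read the bracket in the 9.3.1 formula as enclosing the whole difference. The end date minus the randomisation date plus 1 is 10, so the patient has 28 − 10 = 18 ventilator-free days in Table 14.2.3. The same patient is not free of respiratory failure in Table 14.2.2.

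**Size.** Let m be Day 28 mortality and f the share of survivors off all support at Day 28.

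- m = 0.3 to 0.7. Protocol 1.1 gives this range for ICU patients without a time horizon; its use at Day 28 is an assumption.
- f = 0.6 to 0.9. This is an assumption; the documents give no figure.

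| Quantity | Formula | Lowest | Highest | m = 0.5, f = 0.75 |
|---|---|---|---|---|
| Correct | (1−m)f | 0.3 × 0.6 = 18% | 0.7 × 0.9 = 63% | 37.5% |
| As written, on-support survivors have blank end dates | 0 | 0% | 0% | 0% |
| As written, all on-support survivors have a later end date | (1−m)(1−f) | 0.3 × 0.1 = 3% | 0.7 × 0.4 = 28% | 12.5% |
| Sign reversed only, blank end dates | 1−m | 30% | 70% | 50% |

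The last row exceeds the correct value by (1−m)(1−f), which is 3 to 28 percentage points. No patient counts are given, because SAP 12 says the study closed before reaching 70 subjects.

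**The case against.** The reversed sign itself is hard to contest. The fair objections concern how much follows from it.

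- **No code is available.** The documents cannot show that Table 14.2.2 was produced this way. The correct definition stands in three places, and a result near zero might be noticed against Table 14.2.3 or at quality control. This is true, and the finding is conditional on literal programming. Possible later detection does not make the rule right.
- **Case E may be rare.** Participation ends at Day 28, and nothing shows that end dates after the visit are collected. This stands: 0% is the more natural result of the written rule, and 3% to 28% applies only if later dates are entered.
- **The SAS point addresses a repair that nobody has proposed.** It also assumes blank end dates for ongoing records, and the form itself is not available. This is fair as far as it goes. Its use is to show why ongoing support must be coded before any date comparison.
- **The percentages rest on assumed inputs.** Correct. The misclassification of weaned survivors does not depend on them. The 0% also presumes that every survivor has a start date recorded.
- **High-flow oxygen and ECMO may not be on the form.** Listing 16.2.6.1 shows durations only as invasive or not invasive. This deserves checking, but 9.2 already relies on the same form for every type of support.
- **The output is descriptive.** No test, interval or p-value is affected. That limits the damage but does not excuse it, because the percentage is the entire result.

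**Conclusion.** The concern holds. SAP 9.2 is wrong as written, not merely incomplete: followed literally, it codes every survivor weaned before the D28-FU visit as not free of respiratory failure. It must be corrected before Table 14.2.2 is relied on. That conclusion needs only the text of the rule and the fact that eligible patients are ventilated at entry.

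Under the assumed ranges for mortality and weaning, the reported percentage would be 0%, or at most 28%, where the correct value lies between 18% and 63%. The error is confined to the derivation. The endpoint definition is sound, and the survival condition is right.

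**What to change.** Leave the endpoint definition alone and replace the second condition in SAP 9.2 with wording such as:

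> Every Ventilatory Support record of a type named in the endpoint definition (mechanical ventilation, NIV, ECMO, high-flow nasal cannula) has an end date before the D28-FU visit date, and no such record is ongoing at that visit.

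Four points go with it:

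1. Code any ongoing record as not free before comparing dates.
2. State the tie rule expressly. The strict form above codes an end date on the visit day as not free, which matches the strict sign in 9.3.9.
3. Resolve closed records with a missing end date at data review before lock and document the decision in the Data Review Report. SAP 7.4 already provides the route: "Other critical missing data, if any, will be discussed during the review of the data before database lock".
4. Confirm against the eCRF that high-flow oxygen and ECMO are recorded on the Ventilatory Support form.

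The cost is a few lines of SAP text and one derivation in the analysis dataset. The rule uses the form that 9.2 already names, so it asks for no data collection beyond what the present rule presupposes. If the tables have already been run, Table 14.2.2 and the matching entries in Listing 16.2.6.2-b should be checked against the corrected rule and rerun if needed, with the change explained in the study report.
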